8.1.2 Adverse Events

An adverse event (AE) is any untoward or unfavorable medical occurrence in a human participant, including any abnormal sign (for example, abnormal physical exam or laboratory finding), symptom, or disease, temporally associated with the participant's participation in the research, whether or not considered related to the participant's participation in the research.

The safety of subdermal injections of Sonazoid was determined in a safety study conducted by our group [Machado et al. 2018]. The study assessed the safety and tolerability of subdermal administration of two dosages Sonazoid (1 and 2 ml) in the breasts of healthy, female volunteers with screening and baseline assessments/procedures that included informed consent, medical history, demography, physical examination, vital signs and a focused physical exam as well as recording of any adverse events (AEs). Only minor local and insignificant adverse experiences confined to the injection site and surrounding area were encountered by the volunteers, local redness was seen in 83% of the cases, local pain in 33% of the cases and local bruising in 25% of the cases [Machado et al. 2018]. All adverse experiences were completely resolved without

any intervention by the time the study was completed as shown in Table 1 (repeated below for convenience).

Sonazoid Intravenous Clinical Safety Trials

Prior to the development of lymphsonography and the subdermal use of UCA, clinical trials were done to evaluate the safety of intravenous use of Sonazoid.

Table 1. Adverse experiences divided by volunteers and by dosage.

Adverse experience	Volunteers (n=12)	1 ml (n=12)	2 ml (n=12)
Redness	10 (83%)	10 (83%)	7 (58%)
Pain	4 (33%)	2 (17%)	3 (25%)
Bruise	3 (25%)	2 (17%)	1 (8%)
Burning sensation	2 (17%)	1 (8%)	2 (17%)
Numbness	1 (8%)	1 (8%)	1 (8%)
Tingling sensation	1 (8%)	0 (0%)	1 (8%)

Sonazoid was administered intravenous (IV) in clinical trials in 1699 patients. In these patients 404 (23.8%) reported at least one AE, while 12 of 62 (19.4%) of patients receiving a placebo reported AEs.

Forty-three (2.5%, 43/1699) subjects experienced serious adverse events (SAEs), including 13 deaths. None of these events were considered by the investigators to be related to Sonazoid. All the SAEs were considered to be caused by the underlying disease or related treatment. In addition, there were no clinically significant trends in laboratory tests, vital signs, ECGs, or physical examination findings. The most commonly noted AEs were headache (3.6%, 62/1699), chest pain (2.3%, 39/1699), abdominal pain (1.5%, 25/1699), diarrhea (1.5%, 25/1699), and nausea (1.6%, 28/1699). The majority of AEs were mild to moderate in severity (92.6%, 652/704).

8.1.3 Serious Adverse Events

A serious adverse event (SAE) is one that meets one or more of the following criteria:

- Results in death
- Is life-threatening (places the participant at immediate risk of death from the event as it occurred)
- Is disabling or incapacitating
- Results in inpatient hospitalization or prolongation of existing hospitalization
- Results in a persistent or significant disability or incapacity
- Results in a congenital anomaly or birth defect

- An important medical event that may not result in death, be life threatening, or require hospitalization may be considered an SAE when, based upon appropriate medical judgment, the event may jeopardize the participant or may require intervention to prevent one of the outcomes listed in this definition.

8.2 Safety Assessment and Follow-Up

The PI will follow AEs with start dates occurring any time after informed consent is obtained until 7 (for non-serious AEs) or 30 days (for SAEs) after the last day of study participation. Events will be followed for outcome information until resolution or stabilization.

8.3 Recording Adverse Events

The following subsections detail what information must be documented for each AE occurring during the time period specified in Section 8.2 Safety Assessment and Follow-Up. If the patient has experienced AE(s), the investigator will record the following information in the AE log:

- The nature of the event(s) will be described by the investigator in precise standard medical terminology (i.e. not necessarily the exact words used by the patient).
- The duration of the event will be described in terms of event onset date and event ended data.
- The intensity of the AE will be described according to Common Terminology Criteria for Adverse Events version 5.0 (CTCAE), for details see National Cancer Institute home page <http://evs.nci.nih.gov/ftp1/CTCAE/About.html> of the AE. The CTCAE displays Grades 1 through 5 with unique clinical descriptions of severity for each AE based on this general guideline:
 - **Grade 1:** Mild; asymptomatic or mild symptoms; clinical or diagnostic observations only; intervention not indicated.
 - **Grade 2:** Moderate; minimal, local or noninvasive intervention indicated; limiting age-appropriate instrumental activities of daily living.
 - **Grade 3:** Severe or medically significant but not immediately life-threatening; hospitalization or prolongation of hospitalization indicated; disabling; limiting self care activities of daily living.
 - **Grade 4:** Life-threatening consequences; urgent intervention indicated.
 - **Grade 5:** Death related to AE.
- The Causal relationship of the event to the study medication will be assessed as one of the following:
 - **Unrelated:** There is not a temporal relationship to investigational product administration (too early, or late, or investigational product not taken), or there is a reasonable causal relationship between noninvestigational product, concurrent disease, or circumstance and the AE.
 - **Unlikely:** There is a temporal relationship to investigational product administration, but there is not a reasonable causal relationship between the investigational product and the AE.
 - **Possible:** There is reasonable causal relationship between the investigational product and the AE. Dechallenge information is lacking or unclear.
 - **Probable:** There is a reasonable causal relationship between the investigational product and the AE. The event responds to dechallenge. Rechallenge is not required.
 - **Definite:** There is a reasonable causal relationship between the investigational product and the AE.

- The Expectedness of the AE
- Action taken
- The outcome of the AE – whether the event is resolved or still ongoing.

8.3.1 Relationship to Study Intervention

The relationship to study intervention or study participation must be assessed and documented for all AEs. Evaluation of relatedness must consider etiologies such as natural history of the underlying disease, concurrent illness, concomitant therapy, study-related procedures, accidents, and other external factors.

The following guidelines are used to assess relationship of an event to study intervention:

1. Related (Possible, Probable, Definite)
 - a. The event is known to occur with the study intervention.
 - b. There is a temporal relationship between the intervention and event onset.
 - c. The event abates when the intervention is discontinued.
 - d. The event reappears upon a re-challenge with the intervention.
2. Not Related (Unlikely, Not Related)
 - a. There is no temporal relationship between the intervention and event onset.
 - b. An alternate etiology has been established.

8.3.2 Expectedness

The PI is responsible for determining whether an AE is expected or unexpected. An AE will be considered unexpected if the nature, severity, or frequency of the event is not consistent with the risk information previously described for the intervention. Risk information to assess expectedness can be obtained from preclinical studies, the investigator's brochure, published medical literature, the protocol, or the informed consent document.

8.3.3 Severity of Event

Adverse events will be graded for severity according to the Common Terminology Criteria for Adverse Events (CTCAE) version 5.0.

8.3.4 Intervention

Any intervention implemented to treat the AE must be documented for all AEs.

8.4 Safety Reporting

All adverse events and serious adverse events that should be reported as defined in section 8.1.1 will be recorded in the patient's CRF. All adverse reaction will be reported according to the CT-3; detailed Guidance on the collection, verification and presentation of adverse event/reaction reports arising from clinical trials on medicinal products for human use. Link:

https://ec.europa.eu/health/sites/health/files/files/eudralex/vol-10/2011_c172_01/2011_c172_01_en.pdf

All events will be graded by the Investigator according to the Common Terminology Criteria for Adverse Events (CTCAE) version 5.0. A grading (severity) scale is provided for each AE term. SAEs must be reported within 24 hours after the site has gained knowledge of the SAE to the IRB, and the FDA. Every SAE must be documented by the investigator on the SAE pages (to be found as part of the CRF). The SAE Report Form must be completed and signed. SAEs and possible SAEs will be reported to the regulatory authorities and IEC according to local regulations and followed-up until the resolution of the event. The initial report shall promptly be followed by detailed, written reports if necessary. The initial and follow-up reports shall identify the trial subjects by unique code numbers assigned to the latter.

The sponsor keeps detailed records of all SAEs reported by the investigators and performs an evaluation with respect to causality and expectedness. Based on, among other, SAE reports the sponsor will evaluate whether the risk/benefit ratio associated with study is changed. We will in all cases follow the ICH Harmonised Guideline Integrated Addendum to ICH E6(R1): Guideline for Good Clinical Practise ICH E6(R2) ICH Consensus Guideline. Link: <https://ichgcp.net/411-safety-reporting/>

8.4.1 Reporting to IRB

8.4.1.1 *Unanticipated Problems*

All incidents or events that meet criteria for unanticipated problems (UAPs) as defined in Section 8.1.1 Unanticipated Problems require the creation and completion of an unanticipated problem report form (OHR-20).

UAPs that pose risk to participants or others, and that are not AEs, will be submitted to the IRB on an OHR-20 form via the eazUP system within 10 working days of the investigator becoming aware of the event.

UAPs that do not pose risk to participants or others will be submitted to the IRB at the next continuing review.

8.4.1.2 *Adverse Events*

Grade 1 AEs will be reported to the IRB at continuing review.

Grade 2 AEs will be reported to the IRB at the time of continuing review.

8.4.1.3 *Serious Adverse Events*

SAEs will be reported to the IRB on OHR-10 forms via the electronic reporting system (eSAEY) according to the required time frames described below.

Grade 3-4 AEs that are unexpected and deemed to be at least possibly related to the study will be reported to the IRB within 2 working days of knowledge of the event.

Grade 3-4 AEs that are deemed unrelated to the study will be reported to the IRB within 5 working days.

Grade 5 AEs will be reported to the IRB within one working day of knowledge of the event.

All SAEs will be submitted to the IRB at continuing review, including those that were reported previously.

8.4.2 Reporting to SKCC DSMC

All AEs and SAEs, safety and toxicity data, and any corrective actions will be submitted to the DSMC per the frequency described in the SKCC DSMP. The report to the SKCC DSMC will also include any unanticipated problems that in the opinion of the PI should be reported to the DSMC.

For expedited reporting requirements, see **Table 2** below:

8.4.1 Reporting to Funding Sponsor

Once a year throughout the clinical trial, the sponsor will provide the Competent Authority with a listing of all suspected serious adverse reactions which have occurred over this period and a report of the subjects' safety. Annual reports are submitted in accordance with ICH guideline E2F - Note for guidance on development safety update reports.

8.4.1 Reporting to FDA

The PI and the SKCC regulatory team will be responsible for submitting annual reports to the FDA on the progress of the study.

8.4.1 Reporting of Pregnancy

Pregnancy is an exclusion criteria.

Table 2: DSMC AE/SAE Reporting Requirements

	Grade 1	Grade 2		Grade 3				Grades 4 and 5
	Unexpected and Expected	Unexpected	Expected	Unexpected		Expected		Unexpected and Expected
				With Hospitalization	Without Hospitalization	With Hospitalization	Without Hospitalization	
Unrelated Unlikely	Reviewed at Quarterly DSMC Meeting and IRB Annual Review	Reviewed at Quarterly DSMC Meeting and IRB Annual Review	Reviewed at Quarterly DSMC Meeting and IRB Annual Review	5 Working Days	Reviewed at Quarterly DSMC Meeting and IRB Annual Review	5 Working Days	Reviewed at Quarterly DSMC Meeting and IRB Annual Review	Phase I - 48 Hours (Death: 24 Hours)
Possible Probably Definite	Reviewed at Quarterly DSMC Meeting and IRB Annual Review	Reviewed at Quarterly DSMC Meeting and IRB Annual Review	Reviewed at Quarterly DSMC Meeting and IRB Annual Review	48 Hours (Death: 24 Hours)	Phase I - 48 Hours	48 Hours (Death: 24 Hours)	Reviewed at Quarterly DSMC Meeting and IRB Annual Review	Phase I and Phase II - 48 Hours (Death: 24 Hours)

8.5 Halting Rules

The whole trial may be discontinued at the discretion of the PI or the sponsor in the event of any of the following:

- Occurrence of AEs unknown to date in respect of their nature, severity and duration
- Medical or ethical reasons affecting the continued performance of the trial

9 Study Oversight

In addition to the PI's responsibility for oversight, study oversight will be under the direction of the SKCC's Data and Safety Monitoring Committee (DSMC). The SKCC DSMC operates in compliance with a Data and Safety Monitoring Plan (DSMP) that is approved by the NCI.

10 Clinical Site Monitoring and Auditing

Clinical site monitoring and auditing is conducted to ensure that the rights of human participants are protected, that the study is implemented in accordance with the protocol and/or other operating procedures, and that the quality and integrity of study data and data collection methods are maintained. Monitoring and auditing for this study will be performed in accordance with the SKCC's Data and Safety Monitoring Plan (DSMP) developed by the SKCC Data and Safety Monitoring Committee (DSMC). The DSMP specifies the frequency of monitoring, monitoring procedures, the level of clinical site monitoring activities (e.g., the percentage of participant data to be reviewed), and the distribution of monitoring reports. Some monitoring activities may be performed remotely, while others will take place at the study site(s). Appropriate staff will conduct monitoring activities and provide reports of the findings and associated action items in accordance with the details described in the SKCC DSMP.

11 Statistical Considerations

The fundamental hypothesis of this project is that lymphosonography can be used to identify SLNs in patients with cervical, vaginal or vulvar cancers with greater success than the standard of care. For this project the standard of care is either blue dye injections (if the subject goes to surgery) or PET-CT results (if the subject goes to chemotherapy) as part of their management.

In this study we do not focus on whether an SLN is correctly identified, as there is no way of knowing that (unless the subject goes for surgery and the SLN has metastatic deposits but this will only be the case for a small subset) and the number of SLNs not identified by lymphosonography or by the standard of care will, for obvious reasons, be unknown. Hence, we presume all identified SLN are correctly identified.

11.1 Study Hypotheses

Primary hypothesis: Does lymphosonography identify more SLNs in patients with cervical, vaginal or vulvar cancer than the standard of care? The fundamental hypothesis is that on average lymphosonography will detect 20% more SLNs than the standard of care.

Secondary hypothesis: Does lymphosonography identify more SLNs with metastatic deposits in patients with cervical, vaginal or vulvar cancer compared to the standard of care? The fundamental hypothesis is that approximately 20% more cancerous SLNs will be detected with CEUS.

H1: On average lymphosonography will detect 20% more SLN than the standard of care (blue dye or PET-CT).

H1₀ The mean number of SLNs per subject identified by lymphosonography is less than 120% of those identified by standard of care.

H1_a The mean number of SLNs per subject identified by lymphosonography is greater than 120% of those identified by standard of care.

H2: On average 20% more cancerous SLNs will be detected by lymphosonography than by standard of care (i.e., blue dye) using pathology as the reference standard.

H2₀ The % of metastatic SLNs identified by lymphosonography is less than 120% of that identified by standard of care.

H2_a The % of metastatic SLNs identified by lymphosonography is greater than 120% of that identified by standard of care.

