11.2 Analysis Plans

Thomas Jefferson University Hospital cares for approximately 200 patients with female lower genital tract cancer per year. The patients studied in this project will be women over the age of 18 who have a diagnosis of cervical, vaginal or vulvar cancer. The patient population of this project will reflect the population demographics found at major American urban academic health centers. The overall TJUH demographics include 60 % Caucasian, 16 % African American, 13 % Hispanic, 5 % Asian, 1 % Other, and 5 % unknown patients. The goal of this pilot study is to enroll 40 patients over 2 years. Given that these women have been diagnosed with cancer, they are usually very motivated to participate in research studies that include additional evaluations and, therefore, we do not expect recruitment to be a major issue.

For the primary hypothesis the number of SLN detected by CEUS will be compared to the number of SLN detected by the standard of care (i.e., by blue dye or by PET-CT) using paired t-test or paired Wilcoxon test (depending on whether the data is normal distributed or not).

For the secondary hypothesis the percentage of SLNs with metastatic deposits identified by lymphosonography and by blue dye will be pairwise compared after eliminating the SLNs identified by both methods using two-sample t-test or Wilcoxon test (again after testing for normalcy). The histopathological assessment of the surgically removed LNs will serve as the reference standard.

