11.4 Sample Size Considerations

The sample size analysis is based on the primary aim of this study (i.e., on Aim 1) and assumes that on average lymphosonography will detect 20% more SLN than the standard of care (blue dye or PET-CT]. Hence, a power analysis was performed using NCSS/PASS 2019 (NCSS, East Kaysville, UT) and a sample size of 40 patients achieves 86.9% power to detect the effect size of

0.5 (i.e., assuming the 20% more detected SLN with CEUS versus the standard of care techniques, and twice of standard deviation of paired difference) at 5% significance level using a two-sided paired t-test.

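### H1 sets a hurdle of 120% of the standard-of-care count, but the planned paired test and the 86.9% power are for a zero difference, so a significant result would not establish H1

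*Combined protocol and SAP*

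**What the plan says.** Section 11.1 (Study Hypotheses) asks the primary question in words: "Does lymphosonography identify more SLNs in patients with cervical, vaginal or vulvar cancer than the standard of care". That question contains no threshold. The formal pair below it does. H1_0 reads "The mean number of SLNs per subject identified by lymphosonography is less than 120% of those identified by standard of care" and H1_a reads "The mean number of SLNs per subject identified by lymphosonography is greater than 120% of those identified by standard of care".

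Section 11.2 (Analysis Plans) compares the number of nodes found by contrast-enhanced ultrasound (CEUS, i.e. lymphosonography) with the number found by the standard of care (SOC) "using paired t-test or paired Wilcoxon test (depending on whether the data is normal distributed or not"). It gives no multiplier of 1.2, no shifted null value, no ratio estimate and no confidence-limit rule.

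Section 11.4 (Sample Size Considerations) "assumes that on average lymphosonography will detect 20% more SLN than the standard of care" and states that "a sample size of 40 patients achieves 86.9% power to detect the effect size of" 0.5, explained as "assuming the 20% more detected SLN with CEUS versus the standard of care techniques, and twice of standard deviation of paired difference", with a two-sided paired t-test at the 5% level.

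**The concern.** A paired test of two raw counts rejects, or fails to reject, a zero difference, i.e. a ratio of 100%. H1_0 covers every ratio below 120%. Rejecting equality therefore does not reject H1_0, because any true ratio between 1.00 and 1.20 violates equality and still satisfies H1_0.

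The 20% figure also has two incompatible roles. In 11.1 it is the edge of the null. In 11.4 it is the true effect the trial is powered to find. If the test were moved to the 120% null, the planning assumption would sit exactly on that boundary and the assumed effect would be zero.

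At stake is what the trial may conclude on its primary hypothesis. A significant p-value could be read as confirming 20% more sentinel nodes when the true excess is well short of that, and the power that justifies 40 patients would not belong to the hypothesis as written.

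**Working it through.** **Inputs.** From 11.4: n = 40, effect size 0.5, two-sided 5% paired t-test, true ratio 1.20. The wording about the SD is garbled. The only reading that yields 0.5 is an SD of the paired difference equal to twice the 20% difference, i.e. 0.40 × SOC mean (0.20/0.40 = 0.5). From 11.1: null boundary at a ratio of 1.20.

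**Step 1: reproduce the stated power.** Against zero difference, df = 39, noncentrality = 0.5 × √40 = 3.162, critical value t(0.975, 39) = 2.0227. Noncentral-t power = 0.8694, which matches the stated 86.9%. Section 11.2 names no null value, so the zero null is an inference. The match supports it: measured from a 120% null, the assumed effect size would be (1.20 − 1.20)/0.40 = 0.

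**Step 2: how often the planned test is significant when H1_0 is true.** For true ratio r, effect size d = (r − 1)/0.40 and noncentrality = d√40. Probability of significance in favour of CEUS:

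| True ratio r | d | d√40 | Probability | H1_0 |
|---|---|---|---|---|
| 1.10 | 0.250 | 1.581 | 33.8% | true |
| 1.15 | 0.375 | 2.372 | 63.8% | true |
| 1.19 | 0.475 | 3.004 | 83.4% | true |

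**Step 3: the observed excess that decides each claim.** Half-width of the 95% interval = 2.0227 × 0.40/√40 = 0.128.
- Significant against equality: observed ratio above 1 + 0.128 = 1.128.
- Lower limit above 1.20 (taking the SD of CEUS − 1.2 × SOC also as 0.40): observed ratio above 1.20 + 0.128 = 1.328.

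**Step 4: test H1 as written.** Form D* = CEUS − 1.2 × SOC for each patient and test its mean against zero. At the plan's own ratio of 1.20 the mean of D* is zero, so the two-sided 5% test rejects in favour of H1_a with probability 2.5%, whatever the SD (5% for a one-sided 5% test). A simulation of 20,000 trials gave 2.4%.

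At higher ratios an SD for D* is needed, and the documents do not give one. The central assumption is 0.40 × SOC mean, so d = (r − 1.2)/0.40. For the range, write D = CEUS − SOC, so that D* = D − 0.2 × SOC. In units of the SOC mean, Var(D*) = 0.16 − 0.4 × ρ × 0.40 × CV + 0.04 × CV². Assumed values are an SOC coefficient of variation (CV) of 0.3 to 0.7 and a correlation ρ between D and SOC of −0.5 to 0.5, giving SDs from 0.352 to 0.485.

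| True ratio | Power, SD 0.40 | Range over assumptions |
|---|---|---|
| 1.20 | 2.5% | 2.5% |
| 1.30 | 33.8% | 25–42% |
| 1.40 | 86.9% | 72–94% |

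**Step 5: cost of keeping the hurdle.** For 86.9% power at a true ratio of 1.30, d = 0.10/SD. With SD 0.40, d = 0.25; scaling gives 40 × (0.5/0.25)² = 160, and the exact noncentral-t answer is 154 patients. SDs of 0.352 and 0.485 give 120 and 226.

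**The case against.** The best defence is that most of the plan already states the question the test answers. Sections 2.1.1 and 11.1 ask whether CEUS finds more nodes, and section 11 speaks of greater success. The paired test and the power calculation fit that. The formal pair in 11.1 then looks like a drafting slip that turned a planning effect into a null boundary. On that reading the 86.9% stands, and nothing shows the trial to be underpowered for its worded question. This is largely right and decides which repair is natural. It does not remove the conflict: the formal hypotheses are what a p-value is reported against, and nothing in the plan says which version governs.

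A second argument is that this is a single-site pilot, and that no passage equates p<0.05 with a 20% excess. The misreading is indeed a risk, not a stated rule. But the plan sets formal hypotheses, a 5% level and a power figure, and section 11.5 disclaims firm conclusions only for the analyses split by cancer type.

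Third, power against 120% depends on an SD the documents do not supply. That stands, so the figures at 1.30 and 1.40 are given as ranges. The 2.5% at 1.20 is not affected.

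Fourth, restating the null in terms of means fits the t-test branch of 11.2 but not strictly the Wilcoxon branch, and H2 has the same 120% form. Both are fair additions and are taken into the fix.

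**Conclusion.** The concern holds; the plan is wrong as written. The arithmetic in 11.4 is correct, but it answers a hypothesis other than H1. The planned test can be significant with up to 83% probability while H1_0 is true (true ratio 1.19), and a literal test of H1 has a 2.5% chance of success at the plan's assumed effect.

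The conclusion rests on two inferences: that the paired test in 11.2 is against zero, and that the effect size of 0.5 means an SD of 40% of the SOC mean. Both are supported by the exact reproduction of 86.9%. The 2.5% does not depend on the SD. Power at ratios above 1.20 does, and should be read as the ranges shown.

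Because this is the primary hypothesis and determines the permissible claim, it must be corrected before the data are analysed.

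**What to change.** **Preferred.** In 2.1.1 and 11.1, restate H1_0 as equal mean counts per patient (paired difference zero) and H1_a as a difference. In 11.4, describe the 20% only as the planning effect and state the SD assumption plainly (SD of the paired difference equal to twice the assumed difference). The test, n = 40 and the 86.9% then agree. In 11.2, add the ratio of mean counts with a 95% CI by a named method. A Fieller interval suits, since it inverts the paired t-test of CEUS − r × SOC. Allow a claim of 20% more nodes only if the lower limit exceeds 1.20. Rest any statement about means on this interval, whichever of the t-test or Wilcoxon test is used for the p-value.

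**If 120% is truly the hurdle.** Test CEUS − 1.2 × SOC against zero, assign exactly 120% to the null (at present it belongs to neither hypothesis), and replace the 86.9% with power at a stated true ratio above 1.20. With 40 patients that is roughly 25–42% at 1.30, and keeping 86.9% there would take about 154 patients (120 to 226 over the assumed SDs).

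H2_0 and H2_a in 11.1 have the same 120% form, and the H2 comparison in 11.2 has no 1.2 factor either. Align them in the same amendment.

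**Cost.** The preferred option needs wording changes in 2.1.1, 11.1, 11.2 and 11.4 and one extra interval. It adds no patients or procedures. The price is a more modest claim: a significant test shows more nodes, not 20% more.
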